9.3 Disease-Related Events or Outcomes Not Qualifying as AE/SAE's

Not applicable.

9.4 Monitoring and Recording of AEs and SAEs

9.4.1 Adverse Events

Any AE experienced by the subject from Visit 2 (Insertion/Day 1) through Visit 7 (Week 8) is to be recorded in the eCRF, regardless of the severity of the event or its relationship to study treatment.

Any AEs already documented at a previous assessment and designated as ongoing, should be reviewed at subsequent visits as necessary. If these have resolved, this should be documented.

Changes in intensity or frequency of AEs should be recorded as separate events (i.e., a new record started).

9.4.2 Serious Adverse Events

Any SAE experienced by the subject from Visit 2 (Insertion/Day 1) through Visit 7 (Week 8) is to be recorded on an SAE Form, regardless of the severity of the event or its relationship to study treatment.

Any SAE ongoing when the subject completes the study or discontinues from the study will be followed by the Investigator until the event has resolved, stabilized, or returned to baseline status.

9.4.3 All Events

All events must be assessed to determine the following:

- If the event meets the criteria for an SAE as defined in [Section 9.2](#).
- The severity of the event as defined in [Section 9.7.1](#).
- The relationship of the event to study treatment as defined in [Section 9.7.2](#).

9.5 Immediate Reporting of Serious Adverse Events and Pregnancies

In order to adhere to all applicable laws and regulations for reporting an SAE or pregnancy, the study site must formally notify the pharmacovigilance team within 24 hours of the study site staff becoming aware of the SAE or pregnancy. It is the Investigator's responsibility to ensure that the SAE or pregnancy reporting information is emailed or faxed as described in Figure 3. It may be necessary for the pharmacovigilance team to directly communicate with the Investigator if additional information is required.

After the initial SAE report, the investigator is required to proactively follow each subject and provide further information to the pharmacovigilance team on the subject's condition within 24 hours. New or updated information will be recorded on the SAE reporting form. The updated SAE reporting form should be sent to the pharmacovigilance team within 24 hours as described in Figure 2.

All additional follow-up evaluations must be reported to the pharmacovigilance team. Such data should be sent by fax or email (Figure 3) within 10 calendar days. All SAEs will be followed until the Investigator and Ocular Therapeutix agree that the event is satisfactorily resolved.

9.6 Death

The death must be recorded on the appropriate eCRF. All causes of death must be reported as SAEs. The Investigator should make every effort to obtain and send death certificates and autopsy reports to the pharmacovigilance team.

Figure 3 Reporting Information for SAEs and Pregnancies

To report initial or follow up SAE or Pregnancy information email or fax a copy of the SAE or Pregnancy report form to the following:

ProPharma Group

Email: [contact]

[contact]

9.7 Evaluating AEs and SAEs

9.7.1 Severity

The following definitions should be considered when evaluating the severity of AEs and SAEs.

Mild Event is noticeable to the subject, but is easily tolerated and does not interfere with the subject's daily activities

Moderate Event is bothersome, possibly requiring additional therapy, and may interfere with the subject's daily activities

Severe Event is intolerable, necessitates additional therapy or alteration of therapy, and interferes with the subject's daily activities.

For AEs that change in intensity, the start and stop date of each intensity should be recorded.

An AE that is assessed as severe should not be confused with a SAE. An event is defined as 'serious' when it meets one of the pre-defined outcomes as described in [Section 9.2](#) Definition of a SAE.

9.7.2 Relationship to OTX-DED or Hydrogel Vehicle product or procedure

The following definitions should be considered when evaluating the relationship of AEs and SAEs to the study treatment:

Unrelated	This category applies to those (S)AEs which, after careful consideration, are clearly and incontrovertibly due to extraneous causes (disease, environment, etc.); there is no reasonable probability that the (S)AE may have been caused by the insertion procedure or the ophthalmic insert. If the investigator determines that the AE is unlikely to be related to the study drug, then this would be the appropriate category.
Related	The following criteria should be applied in considering inclusion of an (S)AE in this

	
category:
 
i. It bears a reasonable temporal relationship to the insertion procedure or the presence of the ophthalmic insertii. It could not be reasonably explained by the known characteristics of the subject's clinical state, environmental or toxic factors or other factors (e.g., disease under study, concurrent disease(s) and concomitant medications) and modes of therapy administered to the subjectiii. It disappears or decreases on removal of the ophthalmic insertiv. It follows a known pattern of response to the insertion procedure or the ophthalmic insert
--	---

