4.9.1. Adverse Events

Adverse events will be coded using MedDRA Version 24.0 – Mar 2021 and displayed in tables and listings using System Organ Class (SOC) and Preferred Term (PT).

Analyses of adverse events will be performed for those events that are considered treatment emergent adverse events (TEAE), where treatment emergent is defined as any adverse event

Statistical Analysis Plan

Sponsor:	Ocular Therapeutix, Inc.		
Protocol:	OTX-DED-2020-201		
Document Version No.:	V1.0	Document Date:	11NOV2021

with onset on or after the first dose of study medication through the end of the study or any event that was present at baseline but worsened in intensity or was considered drug-related by the investigator through the end of the study.

The safety will be assessed by incidence of TEAEs, therefore, in any tabulation, a subject contributes only once to the count for a given adverse event (SOC or preferred term). An overall summary of TEAEs will be presented including the number of events and the number of the subjects with events along with percentages by treatment group and overall. The overall summary will include subjects with AE leading to death, subjects with TEAEs leading to insert removal and subjects with TEAEs leading to subject withdrawal. In summary tables, SOC will be presented alphabetically and events within SOC will be presented by decreasing frequency count based on the total column.

The frequency and percentage of subjects with any TEAE, any serious TEAE, any TEAEs by relationship to treatment (unrelated, related), any serious TEAEs by relationship to treatment (unrelated, related), any TEAE by severity (mild, moderate, or severe) will be summarized separately for ocular and non-ocular events by treatment group and overall. Separate summaries for ocular TEAEs and non-ocular TEAEs by preferred terms in decreasing frequency based on all subjects will be tabulated.

All adverse events will be listed in subject data listings.

By-subject listings also will be provided for the following: subject deaths; serious adverse events; and adverse events leading to withdrawal.

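### Protocol 9.7.2 sets two inconsistent thresholds for an unrelated adverse event, and the lower one leaves out the insertion procedure

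*Protocol*

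**What the plan says.** Protocol 9.4.3 requires every adverse event to be assessed for its relationship to study treatment as defined in section 9.7.2. That section is titled "Relationship to OTX-DED or Hydrogel Vehicle product or procedure" and offers two classes.

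- ***Unrelated*, opening sentence.** "This category applies to those (S)AEs which, after careful consideration, are clearly and incontrovertibly due to extraneous causes". The same sentence goes on to require that "there is no reasonable probability that the (S)AE may have been caused by the insertion procedure or the ophthalmic insert".
- ***Unrelated*, last sentence.** "If the investigator determines that the AE is unlikely to be related to the study drug, then this would be the appropriate category".
- ***Related*.** The entry begins "The following criteria should be applied in considering inclusion of an (S)AE in this" category and lists four criteria. Criterion i concerns timing relative to the insertion procedure or the presence of the insert. Criterion iv reads "It follows a known pattern of response to the insertion procedure or the ophthalmic insert".

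Protocol 4.4 lists 13 risks already observed with the insertion procedure, among them eye pain and trauma to the punctum. SAP 4.9.1 gives the number and percentage of subjects with "any TEAEs by relationship to treatment (unrelated, related"), and does the same for serious TEAEs, separately for ocular and non-ocular events. Its definition of a treatment-emergent event also has a limb that turns on whether the investigator considered the event drug-related; that limb does not mention the procedure.

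**The concern.** The two *Unrelated* sentences differ in two ways. The first is the degree of certainty: the opening sentence demands that another cause be beyond dispute, while the last asks only that a connection be unlikely. The second is the exposure: the opening sentence names the procedure and the insert, while the last names the study drug and says nothing of the procedure.

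The events caught between them are foreseeable, because this product is delivered by a physical procedure with its own list of known risks. The study is not powered for efficacy, and Protocol 10.3 gives the collection of safety information as a reason for its size. The share of events attributed to treatment is thus one of the results that later trials will draw on. If investigators follow different sentences, that share depends partly on which sentence each of them applied.

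**Working it through.** The plan states no figure for this point, so the check is mainly a comparison of texts.

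**Step 1. The two sentences side by side**

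| | Opening sentence | Last sentence |
|---|---|---|
| Certainty needed for *Unrelated* | Outside cause beyond dispute; no reasonable probability of causation | Connection merely unlikely |
| Exposure considered | Insertion procedure or insert | Study drug |
| Procedure named | Yes | No |

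An event that meets the last sentence need not meet the opening one. Nothing in 9.7.2 says which prevails, and SAP 4.9.1 gives no rule for resolving the conflict.

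**Step 2. A test case from the plan's own risk list**

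Take trauma to the punctum during placement, one of the insertion risks in Protocol 4.4.

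- *Opening sentence:* the procedure is a plausible cause, so the event is not *Unrelated*.
- *Related criterion i:* the timing fits the procedure. Met.
- *Related criterion iv:* it is a known response to the procedure. Met.
- *Last sentence:* an investigator who judges the event unlikely to be due to the study drug is directed to *Unrelated*.

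The same event reaches both classes, each by following a sentence of 9.7.2.

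**Step 3. Does the meaning of study drug remove the conflict?**

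- Read narrowly, as dexamethasone, the last sentence omits both the insert and the procedure.
- Read broadly, as the supplied product, it covers the insert but still omits the procedure, and it still sets the lower bar.

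The conflict remains under either reading.

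**Step 4. Size of one reclassification**

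Inputs: about 150 subjects, 50 planned per arm, about 15 sites (Protocol 6.1). SAP 4.9.1 counts each subject once, so the unit is a subject whose only related event changes class.

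- Per arm: 1/50 = 0.02, or 2.0 percentage points.
- Overall: 1/150 = 0.0067, or 0.67 percentage points.

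The documents give no rate of procedure events. Purely as an assumption, if 1 to 5 subjects in an arm were affected, the arm's related rate would differ by 1/50 = 2 points to 5/50 = 10 points according to which sentence was applied. That range illustrates scale and is not an estimate.

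**The case against.** The best answer is that the cell should be read as a whole. The section title, the opening *Unrelated* sentence and *Related* criteria i and iv all bring in the procedure, so a sensible investigator would not use the last sentence to set a procedure event aside. That is fair as a reading of intent, and nothing in the protocol expressly permits procedure events to be filed as unrelated. But the last sentence is worded as a direction to use the category, and an investigator who applies it literally is following the text.

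Several stronger conclusions are tempting, and the documents do not support them:

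- **That the last sentence tests dexamethasone alone.** Protocol 6.6 and 7.6 and SAP 4.6 use study drug for the supplied product or the insert. What is certainly missing is the procedure.
- **That the related/unrelated tables cannot be reproduced.** They can be regenerated exactly from the recorded flags. Only consistency of classification between investigators is in doubt.
- **That procedure harm is hidden.** Protocol 9.4.1 and 9.4.2 require AEs and SAEs to be recorded whatever their relationship, and SAP 4.9.1 tabulates TEAEs overall, by severity and by preferred term, and lists all events. The harm may be misattributed; it does not disappear.
- **That reportable serious reactions would be missed.** Under Protocol 9.9.3 the sponsor's judgement can also trigger a SUSAR, so an investigator's *Unrelated* is not final.
- **That all four *Related* criteria must be met, or that the removal criterion is unusable.** The criteria are introduced as matters to apply when considering the category. Removal is provided for in Protocol 7.6 and Appendix 13.
- **That the arms are compared unfairly.** All three arms undergo insertion under masking, and no difference in procedure-event rates is shown.

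**Conclusion.** The concern holds as an internal contradiction in Protocol 9.7.2. *Unrelated* carries two thresholds, and the lower one omits the procedure. The consequence is that absolute related-TEAE rates under SAP 4.9.1 may be understated, and similar events may be classified differently across about 15 sites.

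Each affected subject is worth 2 percentage points in an arm of 50. That figure assumes the planned arm size and that the subject has no other related event in the same table. The total effect is unknown because the number of such subjects cannot be derived from the documents.

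The matter is limited to causality attribution in descriptive safety tables. Overall event counts and listings, and the efficacy analyses, do not depend on it. It merits correction because the inconsistency sits in a stated rule that every event passes through, and because one sentence repairs it.

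**What to change.** 1. In Protocol 9.7.2, delete the last sentence of the *Unrelated* entry, or reword it so that one threshold applies: *Unrelated* only when there is no reasonable possibility that the drug, the insert or the insertion procedure caused the event. State that all other events are *Related*.
2. Bring the eCRF completion guidance into line with that threshold.
3. In SAP 4.9.1, align the drug-related wording in the TEAE definition so that it refers to the same relationship and includes the procedure.

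Recording relationship to product and to procedure in separate fields would make the tables more informative, but it is optional. The section title fits a combined assessment equally well, and the eCRF is not among the documents, so it may already separate the two.

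The cost is a change of wording and of site guidance. The related-event count may come out slightly higher. No treatment, visit or efficacy analysis changes.

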9.7.3 Expectedness of Events

Expectedness of all AEs will be determined according to the Investigator's Brochure as determined by Ocular Therapeutix, Inc.

9.8 Pre-scheduled or elective Procedures or Routinely Scheduled Treatments

A pre-scheduled or elective procedure or routinely scheduled treatment will not be allowed during the study period.

9.9 Procedures for Handling Special Situations

9.9.1 Pregnancy

Females should not become pregnant during the study period. If this occurs the subject should notify the Investigator immediately. The Investigator must report the pregnancy as outlined in [Section 9.5](#). In addition, the Investigator or study site staff must report the outcome of the pregnancy to the pharmacovigilance team.

9.9.2 Unmasking for Medical Emergencies

In the case of a medical emergency or occurrence of an SAE, the randomization code may be unmasked and made available to the Investigator, Sponsor, and/or other study personnel involved in the conduct of the study. In the absence of medical need, the randomization code will not be available to the above individuals until after the study is completed and the database is locked.

In the event of a medical need, the Investigator will treat each subject, as medically required. If the Investigator feels it is necessary to unmask a subject's treatment assignment after an emergency situation, the Investigator may call the Medical Monitor and notify the Sponsor. The treatment assignment will be revealed on a subject-by-subject basis with the approval of the Medical Monitor and Sponsor, leaving the masking of the remaining subjects intact. Ocular Therapeutix will make the final determination if the unmasking request will be granted. Once the unmasking request is granted the investigator or designee should use the IRT system to unmask the subject's randomization code. The investigator must also indicate in source documents and in the eCRF that the mask was broken and provide the date, time, and reason for breaking the mask. Any AE or SAE associated with breaking the mask must be recorded and reported as specified in this protocol.

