4.4 Risk-Benefit Analysis

OTX-DED has several potential advantages over topical corticosteroid drops, assuming such a treatment is approved for the signs and symptoms of dry eye disease, given that OTX-DED does not contain any anti-microbial preservatives, may treat the signs and symptoms of episodic dry eye with a single application that is relatively easy to insert, eliminates complexity with daily drops, and delivers therapeutic levels of dexamethasone continuously for the intended duration of therapy. OTX-DED combines two currently used therapies for DED (steroid and punctal plug occlusion).

Based on several decades of use of topical ocular corticosteroids, risks have been identified with the use of dexamethasone, some of which have been observed in clinical trials with the higher dose 0.4 mg dexamethasone insert.

The following AEs and/or risks have been observed with the administration of corticosteroids:

1. IOP Increase/Glaucoma/Ocular hypertension
2. Masking of infection or enhancing existing infections
3. Delayed healing
4. Cataracts

The following AEs and/or risks have been observed with the insertion procedure of the intracanalicular insert:

1. Eye pain and discomfort, including foreign body sensation
2. Tearing or epiphora (with or without mucopurulent discharge)
3. Stenosis
4. Inability to remove test article
5. Perforation of or trauma to the punctum and/or surrounding tissues
6. Punctoplasty
7. Eye inflammation
8. Allergic reaction
9. Dacrocystitis
10. Canalicularitis
11. Decreased/impaired visual acuity
12. Infection or intraocular infection that if severe could lead to temporary or permanent impairment of eyesight

13. Need for surgery on the lacrimal system

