6.3 Randomization and Masking

Subjects will be randomized to treatment assignment. If unmasking is required, the integrity of the study assessments and objectives will be maintained by limiting access to the unmasked data.

A randomization schedule will be computer-generated by a qualified biostatistician independent of the study conduct or project team and uploaded into the EDC system. The EDC/IRT system will be used for randomization and unmasking.

The OTX-DED and HV inserts administered to subjects at randomization in the double-masked treatment phase will be comparable in appearance. Study subjects and investigators and their staff will be masked to the identity of treatment until the final database is locked. The Sponsor's personnel involved with the conduct and monitoring of the study will remain masked until completion of the study and database lock.

Appropriate precautions must be taken to prevent unauthorized access to the randomization scheme. Unless the subject's safety requires otherwise and if time permits, the decision to unmask a treatment assignment is to be made jointly by the Investigator and Sponsor's medical monitor.

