7.6 Withdrawal Criteria

Any subject who wishes to voluntarily discontinue study drug or withdraw from participation in the study for any reason is entitled to do so without obligation.

IP may be discontinued (insert removed [see [Appendix 13](#)]) and any subject may be discontinued from study participation at any time during the study at the discretion of the Investigator or the Sponsor for any reason.

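### The emergency unmasking procedure in Protocol 9.9.2 requires Medical Monitor and Sponsor approval and omits the safety and time exception given in Protocol 6.3 and SAP 2.4

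*Protocol*

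**What the plan says.** Protocol 9.9.2 (Unmasking for Medical Emergencies) begins by allowing the code to be broken in a medical emergency or after an SAE. It then describes one route. The investigator may call the Medical Monitor and notify the Sponsor, and the assignment is revealed "with the approval of the Medical Monitor and Sponsor". The last word lies with the company: "Ocular Therapeutix will make the final determination if the unmasking request will be granted". The IRT step comes only after that ("Once the unmasking request is granted the investigator or designee should use the IRT system to unmask"). The section gives no exception for urgency, no response time, and no fallback if the approvers cannot be reached. It does say that "the Investigator will treat each subject, as medically required", and it requires the date, time and reason for any code break to be documented.

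Protocol 6.3 (Randomization and Masking) has a different rule, with an exception built in: "safety requires otherwise and if time permits, the decision to unmask a treatment assignment is to be made jointly by the Investigator". The sentence opens with an unless clause about the subject and closes by naming the medical monitor as the other party to the decision. SAP 2.4 repeats it.

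**The concern.** The general section on masking relaxes the consultation requirement when safety or time demands it. The section written for emergencies does not, and it adds a Sponsor decision that the general section lacks. Site staff facing an emergency would naturally turn to 9.9.2, which tells them to obtain a grant before using the IRT.

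What is at stake is prompt knowledge of the assignment, and any care that depends on knowing whether the insert contains a corticosteroid. Protocol 4.4 lists "Masking of infection or enhancing existing infections" and IOP increase among the corticosteroid risks. It lists "Inability to remove test article" among the insertion risks, so taking the insert out may not always be possible.

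**Working it through.** The plan states no figure to reproduce. The check is a comparison of the three sections, followed by simple arithmetic on exposure.

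**Comparison of the rules**

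| Question | Protocol 9.9.2 | Protocol 6.3 and SAP 2.4 |
|---|---|---|
| Who must agree? | Medical Monitor and Sponsor | Investigator and medical monitor jointly |
| Who has the last word? | Sponsor | Nobody named beyond the joint decision |
| Exception for safety or lack of time? | None stated | Yes |
| When is the IRT used? | After the request is granted | Order not stated; Protocol 6.3 and SAP 2.3 name the EDC/IRT as the unmasking tool |
| Who breaks the code if the exception applies? | Not addressed | Not stated |
| Cross-reference or precedence rule? | None | None |

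**Two readings of 9.9.2**

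1. The approval route covers the emergency itself, as the section's title and opening sentence suggest. It then conflicts with the exception in 6.3.
2. The approval route covers only requests made once an emergency has occurred, as one sentence in 9.9.2 can be read. Then 9.9.2 contains no procedure for unmasking during the emergency. Section 6.3 lifts the joint decision but does not say who may act in its place.

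Under either reading, the investigator has no stated direct route to the code.

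**What need not wait.** Section 9.9.2 leaves treatment to the investigator. Section 7.6 ("IP may be discontinued (insert removed" being its term for stopping treatment) permits removal at the investigator's discretion without unmasking. Only access to the assignment, and care that depends on it, can be held up.

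**Exposure**

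- Planned allocation (Protocol 6.1, Table 2): 50 on 0.2 mg, 50 on 0.3 mg, 50 on vehicle.
- Steroid arms: 50 + 50 = 100; 100/150 = 66.7%.
- Vehicle: 50/150 = 33.3%.
- Active and vehicle inserts are made to look alike (Protocol 6.3), so neither possibility can be ruled out without the code.
- AEs and SAEs are recorded from Day 1 to the final visit, planned for Day 57 with a window of 10 days: 57 + 10 = Day 67 at the latest.
- Designed release (Protocol 4.2) is up to 14 days for 0.2 mg and up to 21 days for 0.3 mg. That steroid content matters most in this period is an inference from the release design; the protocol does not say so.

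These figures show who is exposed and for how long. They do not measure the length of a delay, how often one would occur, or the harm it would cause.

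**The case against.** The strongest reply is that the sections can be read together. Section 6.3 sets a protocol-wide rule that 9.9.2 does not revoke. The opening sentence of 9.9.2 permits unmasking in an emergency without any approval condition, and the approval steps belong to later requests. On this view the wording is unclear, but urgent unmasking is not in fact conditional on approval. This reading is possible, but neither document states it, and it still leaves the investigator without a described route during the emergency.

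The second reply is that no specific care depending on the code has been identified. For suspected infection or raised IOP, a clinician can treat, try to remove the insert, and presume steroid, which is the more likely assignment at 2:1. The insert is local, its dose is below the marketed 0.4 mg strength, and the dog toxicology study in Protocol 4.3 showed no systemic toxicity. Failure to remove the insert is an insertion risk that has nothing to do with its steroid content. This stands as a limit on how serious the point is. It does not justify a procedure that makes the code subject to a grant with no limit to non-urgent requests.

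Third, operational detail may sit in the IRT set-up or the monitoring plan, which are not available here. Whether the IRT actually blocks the investigator before approval is unknown, so the delay is a reasonable inference and has not been demonstrated. The protocol is nevertheless what sites are told to follow.

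**Conclusion.** The point holds. The protocol's only procedure headed for medical emergencies makes access to the assignment depend on approval, gives the Sponsor the last word, and omits the exception found in Protocol 6.3 and SAP 2.4. The Sponsor should correct it. This is a subject-safety and clarity issue; sample size, alpha, power and treatment estimates are untouched. Its practical size cannot be quantified from the documents, and the need may be rare in a short study of a low-dose local insert. The conclusion assumes that sites follow 9.9.2 as written and that no document outside the protocol and SAP gives investigators an independent code break. Confidence is medium, because the more lenient reading cannot be excluded.

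**What to change.** Add to 9.9.2 a sentence to this effect: when the assignment is needed for a subject's urgent care, the investigator may break the code directly in the IRT without prior approval, then promptly notifies the Medical Monitor and Sponsor and documents the date, time and reason. Limit the approval route and the Sponsor's decision to non-urgent requests. State the same rule in 6.3, so that it is clear who acts when the exception applies. SAP 2.4 already contains the exception and does not direct site conduct, so it needs no substantive change; a pointer to the amended protocol text would keep the two aligned.

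The cost is about one sentence in each of the two protocol sections, with no change to sample size or analyses. The downside is a small risk of additional unmaskings. The urgent-care condition limits this, as does the documentation that 9.9.2 already requires.
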